2.3.4 VULNERABLE SUBJECTS

The study will include children and adolescents 6 to 17 years old at study entry (index visit). Aims of the study are to improve BP care and HTN recognition in children and adolescents, as they are a population at risk for having their HTN not clinically recognized. As such, it is necessary that this study involves children as research subjects. This study is minimal risk as our intervention promotes care that is consistent with national guidelines. It is important to systematically address elevated BP and HTN in this age-group, as children and adolescents have been excluded or underrepresented in previous research studies. To ensure that CDS recommendations for identification and management of elevated BP are appropriate for these patients, we will exclude pregnant or postpartum adolescents. Patients with a known HTN diagnosis or those taking antihypertensive medication will still qualify for CDS-triggered alerts but, because their HTN is not new-onset, they will be excluded from analyses.

The study is specifically designed to include study subjects age 6-17 years old at entry, with up to 12 months of subsequent follow-up. Thus, all patient study subjects are classified as children when they enter the study. There are a number of clear and compelling reasons why those under age 18 years are included in this study:

1. Elevated BP in children and adolescents is associated with elevated BP in adulthood and with subsequent increased risk of untoward clinical events related to elevated BP (strokes, renal failure, myocardial infarction) later in life.
2. Identification and clinical care for elevated BP and HTN in children and adolescents is far from what is currently recommended by the 2017 Guidelines. Thus, research to guide care improvement is justified and necessary. To identify those with elevated BP, providers must interpret measured BP values in the context of age, gender, and height percentile. EHR technology provides a powerful tool ideally suited to translate raw BP data into BP percentile data, and to assess patterns of data over multiple visits to correctly classify those with elevated BP or HTN. The same technology can then be used to provide patient-specific point-of-care clinical decision support based on correct BP classification and the 2017 Guidelines.
3. Because both the definition of elevated BP and BP-related care recommendations are substantively different for children, adolescents and adults, it is important to conduct research specifically with children and adolescents.

Therefore, it is very appropriate to conduct this research project with children and adolescents and their care providers to address distinct problems related to elevated BP and HTN in adolescents.

[name], study Co-PI is a Board-certified pediatrician and subspecialty Boarded in Adolescent Medicine. She has over 15 years prior experience conducting research in children and adolescents, including 2 large NIH-funded cluster randomized trials using CDS tools to improve pediatric care.

[name], study Co-PI is a Board-certified cardiologist and medical director of heart and vascular research at a large rural healthcare system. She has a Master of Public Health in epidemiology and is an expert in cardiovascular disease prevention and clinical trials, including site PI of multiple pragmatic randomized clinical trials through Patient-Centered Outcome Research Institute (PCORI) aimed at reducing cardiovascular disease burden.

3 OBJECTIVES AND ENDPOINTS

Overall goals are to evaluate the effectiveness of the PedsBP CDS and to compare low- and high-intensity approaches to CDS implementation. We will adapt the PedsBP CDS for use at Essentia Health and to measure the implementation processes and outcomes.

We may use the GUIDES checklist to assist us in improving use of the CDS, and will frame our implementation based on the following four domains: 1) CDS context, 2) CDS content, 3) CDS system, and 4) CDS implementation.⁷¹

There are two primary outcomes. One is repeat BP measurement during the same clinic visit, of an initial BP that is ≥ 95 th percentile for children 6-12 years or $\geq 130/80$ mmHg for adolescents 13-17 years. Repeat BPs can be measured by providers or rooming staff but will only contribute to this outcome if recorded in the vitals section of the EHR. The other primary outcome is clinical recognition of HTN within 6 months of meeting criteria for HTN. Post-implementation comparisons of high- plus low-intensity implementation versus usual care and high- versus low-intensity implementation interventions will be conducted for the primary endpoints of BP remeasurement at the index visit (for patients with an elevated first BP), and BP recognition within 6 months of the index visit (for patients newly meeting HTN criteria).

In secondary analyses we will evaluate the impact of the adapted PedsBP CDS on management of HTN including diet and exercise counseling, provision of antihypertensive medications, subspecialty referrals, and diagnostic testing. In

addition, among youth newly meeting criteria for HTN, we will explore differences in BP control at 12 months. This research builds on prior research in pediatric and adolescent HTN^{10,16,23,31,32}, cardiovascular disease,^{33,34} and CDS development and implementation.^{22,24,35} Our multidisciplinary team seeks to improve the quality of BP measurement, increase HTN recognition, and promote guideline adherent management of HTN in rural youth — all necessary first steps towards improving cardiovascular health in this population.

4 STUDY DESIGN

4.1 APPROACH TO ADAPTATION AND IMPLEMENTATION

4.1.1 PHASE 1 – ORGANIZATIONAL ENGAGEMENT AND PILOT TESTING

Organizational Engagement

We will engage EH clinic leadership and managers, informatics personnel, providers, and rooming staff, through meetings to review standard clinical workflow (e.g., timing of: BP measurement, height measurement, entry of height and BP data into the EHR, and clinician review of EHR data) along with variance in these processes across clinical sites. As in our prior studies, we will work with leadership to identify potential barriers and facilitators that would influence adoption of the CDS.⁹⁶ All PedsBP algorithms and interfaces will be extensively reviewed by EH stakeholders prior to implementation. EH has 18 volunteer patient advisory councils that engage patients and families as advisors, mentors, and educators. The main goal of this program is to improve the patient and family experience and quality of healthcare. With guidance from our consultant, [name], from the University of Minnesota, the EH research team will recruit representative members to review and critique PedsBP CDS interfaces and associated educational material.

[figure not shown]
Pilot Testing

With approval from clinical leaders to proceed, we will then recruit one rural and one urban EH clinic not in the full intervention study and pilot the PedsBP CDS for up to six months. The purpose of the pilot is to verify that 1) we are capturing all data elements needed for intervention analysis, 2) test all components of the CDS algorithms, to make sure they are working as designed/intended, 3) refine algorithms ahead of full intervention. Additional quality assurance will be done on a random sample of patients identified as eligible for receiving the CDS via chart reviews to ensure data accuracy (see Section 9.1.4 for more on quality assurance and testing). During the pilot we will also conduct in-depth interviews with providers and rooming staff at pilot clinics, asking probing questions (e.g., ‘How does the CDS fit in your workflow?’, ‘Was the CDS useful?’, ‘Was the CDS disruptive?’, ‘Did the CDS help you in making a decision about your patient’s blood pressure management?’, ‘How can the study team facilitate use of the CDS?’) about the PedsBP CDS, aiming to identify facilitators and barriers to use (separate interview-specific protocol will be submitted). Up to six months is allotted for the pilot, allowing for an iterative process of piloting, feedback from providers and rooming staff, modifications to the CDS display, wording of recommendations or criteria for triggering BPAs, as needed, with subsequent piloting of the modified tool. In addition, the long pilot period may be needed to ensure that providers and rooming staff have sufficient exposure to the CDS, including for patients newly meeting criteria for HTN (expected background rate 2-3%). Upon reaching a stable CDS platform with general acceptance from providers and clinic staff, the project will move to Phase 2, the full intervention.

4.1.2 PHASE 2 – FULL INTERVENTION

We will randomize clinics to one of three arms and will utilize the 'Educate' intervention strategy, varying by intensity, as described by Powell et al.⁹⁷ The low-intensity intervention clinics may receive education and training following standard practice for delivering any updates to primary care at EH. Within two weeks of our go-live date, providers and rooming staff would receive an email with links to a short instructional video demonstrating provider and rooming staff roles in the PedsBP CDS. The clinics randomized to the high-intensity implementation may be offered the same e-learning, with reminders to view the online training video using EH's internal learning assignments. In addition, at high-intensity clinics study personnel may conduct in-person or video conference training for available providers and rooming staff. These in-person trainings may occur within eight weeks of our go-live. Following implementation, high-intensity clinic staff may receive monthly email reports showing PedsBP use rates. An example, adapted from an ongoing CDS project at EH, is shown in Figure 1.

Figure 1. Example of Peds & TeenBP Use Report

In addition, the project manager may meet either in-person or remotely with each high-intensity clinic's nurse manager monthly throughout the intervention period to assess continued use of PedsBP and to gather feedback ensuring real-time observation of implementation fidelity. Support from EH leaders and clinic providers, along with monitoring and feedback, will help maximize adoption of PedsBP, as demonstrated by CDS use at 75%-80% of targeted visits in previous projects.

To further encourage use of the tool, high-intensity clinics may be offered a best practice 'lunch and learn' for CDS usage at goal. If a clinic achieves four non-consecutive months at or above 75% usage rate, the PedsBP team will provide a catered project-related meeting. The team will provide a meeting agenda for the clinic manager and/or nurse supervisor with the expectation that notes from the meeting will be returned to the team. This 'lunch and learn' may also be offered at 10 non-consecutive months at or above 75% CDS usage.

4.1.3 PHASE 3 – ANALYSES

This period encompasses analyses, reporting of key study results, and implementation of the intervention in the non-intervention clinics, if requested by EH. Throughout the study, there will be ongoing analysis of data as they become available, and preliminary results will be presented at meetings and/or reported in peer-reviewed articles.

5 STUDY POPULATION

In this study, we aim to evaluate the PedsBP CDS in up to 45 primary care clinics with an estimated total of 216 primary care providers and 360 rooming staff. The majority of sites are staffed by family practice physicians (n=31). Pediatricians (n=2), both family practice and pediatricians (n=4) or advanced practice providers alone (n=8) cover the remaining sites.

Based on prep data, we estimate that over the 18-month study period there will be 44,061 unique patients 6-17 years with BP, height and weight recorded, with an average of 2.02 visits per patient over the study period. Similar to demographics of the region, the population is 90% white, non-Hispanic. Fifteen percent of youth receiving care at these sites are obese, with BMI $\geq 95^{\text{th}}$ percentile. Elevated BP is common (10-20% of patients with at least 1 BP meeting

criteria for elevated BP), yet diagnoses for hypertension were only found in 120 (<0.3%).

5.1 INCLUSION CRITERIA

Patients will be eligible for the PedsBP CDS tool if:

- a) 6-17 years of age
- b) BP measured and entered in the vital sign section during an ambulatory primary care visit in a randomized primary care clinic
- c) not pregnant or postpartum

Patients must meet these eligibility criteria to be included into study analyses:

- a) have at least one index visit to a randomized primary care clinic in the intervention period
- b) meet eligibility for PedsBP CDS at index visit
- c) no previous HTN diagnosis prior to index visit
- d) not taking antihypertensive medication prior to index visit
- e) not opted out of use of their data for research via general consent prior to performing analyses

Primary care providers must meet these eligibility criteria to participate in this study:

- a) practice at a randomized primary care clinic
- b) be a pediatric or family medicine care provider (pediatrician, family physician, nurse practitioner or physician assistant), and
- c) provide ongoing clinical care for children and adolescents

Provider and rooming staff inclusion criteria for interviews and surveys are provided in separate protocols.

5.2 EXCLUSION CRITERIA

Patients will be excluded from analyses if the following criteria are met:

- a) outside of the inclusion age range (<6 years and ≥ 18 years) at index visit
- b) pregnant or postpartum adolescents during study period
- c) known HTN diagnosis or taking antihypertensive medication at index visit
- d) opted out of use of their data for research via general consent prior to performing analyses

Provider and rooming staff exclusion criteria for interviews and surveys are provided in separate protocols.

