6.1.1 DESCRIPTION OF CDS INTERVENTION

The PedsBP CDS will be integrated within the EHR (EPICare, Verona, WI) with data transfer to and from a web service, based at HP, for data processing. PedsBP CDS will be activated when a patient 6-17 years has a BP measured and entered in the vital sign section of the EHR during an ambulatory primary care visit in a randomized study clinic. Eligible patients will be allocated to the study arm assigned to their clinic at their index visit. Figure 2 illustrates how data would flow from the EHR to and from the HP-based web-service for the proposed study.

The PedsBP CDS tool includes seven key features:

- (i) a best practice advisory (BPA) regarding the need for height data to classify the BP by percentile
- (ii) a BPA to repeat any BP that is $\geq 95^{\text{th}}$ percentile or $\geq 130/80$ mm Hg
- (iii) classification of current and prior BPs in the prior two years and identification of BPs in stage 1 HTN and stage 2 HTN range
- (iv) review of previous HTN diagnoses and BPs in order to classify an elevated BP at the current or index visit as a first or second elevated BP, or as meeting criteria for HTN
- (v) review of medications and diagnoses that may affect BP
- (vi) tailored CDS based on HTN category and previous diagnoses
- (vii) graphical representation of current and prior BP data by age and BP percentile.

Figure 2. Peds & TeenBP CDS Data Capture

[figure not shown]

Each of these features is described below in Figure 3.

The first component of the CDS is a BPA to ensure a current height measurement for children 12 and under (needed to compute BP percentiles): (a) If a height is entered at the visit, it will be used; (b) If no height is entered when entering a BP, the closest antecedent height recorded within 1 year is used to calculate a BP percentile, assuming a constant height percentile. If there is no height available for the current visit or the prior 12 months, a BPA displays requesting a height be measured and recorded in the EHR. As height measurement is standard in pediatric care, this BPA is currently firing in less than 1% of visits.

The second component of the CDS, a BPA to repeat an elevated BP, is triggered for BPs $\geq 95^{\text{th}}$ percentile in children 6-12 years or $\geq 130/80$ mmHg in youth 13-17 years when the BP is entered into the vital signs section of the EHR, and the vital signs box is closed.

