Data required for PedsBP CDS-enhanced care will be sent to HPI for PedsBP operations. CDS data is retained in the transactional data store with minimal access until needed for analysis. With respect to the transactional data store, the following measures will be taken to protect PCPs and patients from the risk of breach of confidentiality: A unique study ID code unrelated to the medical record number or other study subject-specific information will be assigned to each patient at the index visit (first visit in the intervention period). The study ID is used to link data from patient encounters over time and various data sources that are needed for analysis. All index and subsequent encounter data for eligible patients, including vitals, medications and diagnoses, are securely stored behind a firewall within a limited de-identified dataset.

A crosswalk table linking this code number to a medical record number or patient name will be created by EH programmers in order to 1) check against opt out lists, and 2) link to study outcomes. EIRH Informatics Analysts assigned to this research project will exclude patients who have opted out via general consent; data for these patients will not be stored in analytic data files. The data for patients who have opted out of external research will be deleted from analyses files. The crosswalk will be destroyed within 12 months after completion of the linked databases needed to test study hypotheses. This project will be governed by a Business Associates Agreement, DUA, and appropriate services agreements.

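### Section 5.2(b) excludes patients from the analyses for pregnancy at any time in the study period, although section 5.1 and the neighbouring exclusions are judged at the index visit; the effect is small and re-anchoring one phrase removes it

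*Combined protocol and SAP*

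**What the plan says.** Section 5.1 lists "not pregnant or postpartum" among the conditions for CDS eligibility and then requires, for the analyses, that patients "meet eligibility for PedsBP CDS at index visit". Pregnancy is therefore judged at that visit.

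Section 5.2 lists the exclusions from the analyses. Item (b) is "pregnant or postpartum adolescents during study period". The items on either side are tied to the visit: (a), on age, ends "at index visit", and (c) reads "known HTN diagnosis or taking antihypertensive medication at index visit".

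Section 2.3.4 says "we will exclude pregnant or postpartum adolescents" without a time. The reason it gives is that the CDS recommendations should suit the patients who receive them.

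Section 8.3 describes the "index visit (first visit in the intervention period"). It assesses Aim 1 on care at the visit with the high reading and Aim 2 over the six months after HTN criteria are met. It plans no recall of patients, and it keeps patients with no follow-up visit in Aim 2 on the basis of what was done at the index visit. Section 9.1.1 takes eligibility and outcome data from the EHR. Section 8.4.1 predicts at least one follow-up BP within 12 months for 70% of patients meeting HTN criteria at intervention clinics and 50% at usual care clinics.

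**The concern.** Under 5.2(b) as written, membership of the analysis set depends on something that happens after randomisation and after the index visit. Three consequences follow.

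- **H1/H2.** Re-measurement is settled within the visit. A pregnancy that starts months later cannot have affected it, so deleting the patient loses a valid outcome. The rationale in 2.3.4 does not call for this, because it concerns the advice given at the time.
- **H3/H4.** With EHR data and no recall, a later pregnancy is known only if later care is recorded. An affected patient who returns is removed; one who does not return stays in. If the CDS changes how often hypertensive patients come back, the exclusion could act unequally across arms.
- **Unequal exposure.** Patients indexed early are at risk of exclusion for longer than patients indexed late, and the length of the window is itself unclear.

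Two programmers could also build different primary analysis sets, one from 5.1 and one from 5.2(b).

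**Working it through.** **1. The texts side by side.** Take a patient who is not pregnant at her index visit and becomes pregnant later within the study period. She passes 5.1, because her CDS eligibility is met at the index visit. She passes 5.2(a) and (c), which are judged at the same visit. She fails 5.2(b). The different wording of (b) alone decides whether she is analysed.

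**2. The window.** The introduction to section 5 calls the study period 18 months, and the synopsis dates the 18-month intervention period August 2022 to January 2024. The synopsis also gives patient data collection from 1 August 2022 to 31 July 2025, which is 36 months.

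| Reading of the study period | Indexed August 2022 | Indexed January 2024 |
|---|---|---|
| 18 months | about 18 months at risk of exclusion | one month or less |
| 36 months | about 36 months | about 18 months |

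On either reading, exposure depends on the index date.

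**3. The plan's H3 figures, reproduced.** Inputs from section 8.2: 24 patients per clinic, 15 usual care and 30 CDS clinics, ICC 0.035, two-sided alpha 0.05.

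- Design effect = 1 + (24 − 1) × 0.035 = 1.805.
- Effective sizes: 15 × 24 / 1.805 = 199.4 (usual care) and 30 × 24 / 1.805 = 398.9 (CDS).
- Power for 20% versus 37%, normal approximation for two proportions: 99.3% (plan: 99%).
- Difference detectable with 80% power from 20%: 10.63 points (plan: 11).

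The plan's figures hold, and this point does not dispute them.

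**4. Patients removed under 5.2(b), H3.** The documents give no pregnancy rate. Assume that a share q of the 1,060 patients, equal across arms, has a pregnancy starting after the index visit, with q from 0.5% to 3%. Assume detection of 70% (CDS) and 50% (usual care), borrowing the follow-up BP figures in 8.4.1. Arm sizes are 1,060 / 3 = 353.3 and 2 × 353.3 = 706.7.

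- q = 0.5%: usual care 353.3 × 0.005 × 0.5 = 0.9; CDS 706.7 × 0.005 × 0.7 = 2.5; about 3 in all.
- q = 3%: usual care 353.3 × 0.03 × 0.5 = 5.3; CDS 706.7 × 0.03 × 0.7 = 14.8; about 20 in all.

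**5. Shift in the H3 difference.** Let d be the fraction removed from an arm, p its true recognition (20% or 31%), and r the recognition among those removed. The observed rate is (p − d·r) / (1 − d). At q = 3%, d = 0.015 (usual care) and 0.021 (CDS).

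- r = 0 in both arms: 0.31/0.979 − 0.20/0.985 = 0.3166 − 0.2030 = 0.1136, a shift of +0.36 points from 11.
- r = 1 in both arms: 0.289/0.979 − 0.185/0.985 = 0.2952 − 0.1878 = 0.1074, a shift of −0.26 points.
- At q = 0.5% the same extremes give +0.06 and −0.04 points.

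These limits assume the same r in both arms. The most extreme contrast at q = 3% (everyone removed from usual care recognised, no one removed from CDS recognised) gives 0.3166 − 0.1878 = 0.1288, a shift of +1.9 points; the reverse gives 0.2952 − 0.2030 = 0.0922, a shift of −1.8. Nothing in the plan suggests such a pattern.

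**6. Power.** With 1,060 / 45 = 23.56 patients per clinic, power at 20% versus 31% is 82.15% with no removals, 82.08% at q = 0.5% and 81.74% at q = 3%.

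**7. H1/H2.** No count can be derived. For scale, each 0.1% of the 7,258 expected patients removed costs 7,258 × 0.001, or about 7 completed outcomes.

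**The case against.** The strongest reply is that 5.1 and 5.2 do not strictly contradict each other. Inclusion and exclusion criteria apply jointly, and 5.2(b) may simply be the stricter rule. That is fair, but it makes 5.2(b) the operative rule, so later pregnancies do lead to removal. Item (b) may have been meant as pregnancy at an index visit falling within the study period. The text does not say so, and the explicit anchoring of (a) and (c) speaks against it.

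The second reply is that very few patients are concerned. That stands, and it limits the weight of the point.

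Several stronger readings are tempting, and the documents do not support them:

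- *That 6.1.1 sets a third, conflicting rule.* It says that "PedsBP CDS will be activated when a patient 6-17 years has a BP measured and entered in the vital sign section of the EHR", without mentioning pregnancy. This describes the technical trigger. Eligibility is defined in 5.1, and silence in 6.1.1 is not a competing criterion.
- *That arm comparability is damaged for both primary outcomes.* The 70% and 50% concern follow-up BPs in patients meeting HTN criteria. No expected arm difference in follow-up is given for the wider H1/H2 population.
- *That 0.70 / 0.50 = 1.4 gives the ratio of patients removed.* It is a ratio of detection proportions. With twice as many CDS clinics, the counts would stand at 2 × 1.4 = 2.8.
- *That every patient faces two or three years of exposure, or that any pregnancy in 2024 triggers removal.* On the 18-month reading exposure is at most 18 months, and a pregnancy starting after January 2024 has no effect.

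Even for H3/H4 the follow-up BP figures are only a stand-in, since any care recorded in the EHR could reveal a pregnancy.

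**Conclusion.** The point holds as a defect in the wording of 5.2(b) with a real but small analytic consequence. Read literally, the criterion excludes on a post-index event, over an ambiguous window that varies with index date, and detects it only through later recorded care. For H1/H2 the harm is the loss of completed outcomes, with no arm difference in detection shown. For H3/H4 a difference by arm is plausible but not established.

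The size rests on assumptions: 0.5% to 3% of the H3 cohort affected, equally across arms; detection proportional to the follow-up BP figures; and equal recognition among those removed in both arms. On these, about 3 to 20 of 1,060 patients are lost, the H3 difference moves by at most about 0.4 points against a detectable 11, and power falls by about 0.4 points (82.15% to 81.74%). The trial's conclusions are unlikely to turn on it. The case for acting is that the correction is almost free and fixes the primary analysis sets before the data are analysed.

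**What to change.** Reword 5.2(b) so that it excludes patients *pregnant or postpartum at the visit that defines the outcome*: the elevated-BP visit for H1/H2 and the HTN-criteria visit for H3/H4. Keep patients whose pregnancy begins after that visit. The outcome-defining visit is a better anchor than the first visit of the intervention period, because a patient may meet HTN criteria at a later visit. Give 5.1 and 2.3.4 the same timing so that all three places describe the same patients.

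Optionally, add a sensitivity analysis for H3/H4 and 12-month BP that leaves out patients with a pregnancy recorded within the outcome window (6 and 12 months respectively). It should stay secondary, since it again relies on recorded care. Censoring at pregnancy onset would not suit H3/H4, where the outcome is binary at six months and the planned model is a logistic mixed model.

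The cost is one phrase in 5.2, matching wording in two places and, if wanted, one short additional analysis. No new data are needed.
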